8.7 Clinical Laboratory Tests (Clinical Chemistry, Hematology, Urinalysis)

Clinical laboratory evaluations (clinical chemistry, hematology, and urinalysis) will be performed at Screening, Admission (Day -1), and at Discharge (Day 3), or an early termination assessment will be performed, as applicable.

Out-of-range values and corresponding recheck results will be listed. Other lab results within this panel and time point will also be listed.

For all numeric laboratory values, descriptive statistics will be presented for each laboratory test by study day. Change from baseline will be summarized in a similar manner. Baseline is defined as the result closest and prior to the first product administration, which may include unscheduled or recheck results. This will typically be the result collected on Admission (Day -1). Post product use unscheduled events or rechecks will not be included in summaries. Similarly, early termination results will not be included in summaries.

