8.6 Adverse Events Leading to Discontinuation

Subjects who are discontinued from the study because of an AE will undergo the early termination procedures (section 9.7), as soon as practical after discontinuation and will enter the 3-day Safety follow-up period.

Any AEs or SAEs that are ongoing at the end of the Safety follow-up period will be managed as described in section 8.2.6.

8.7 **Product Events**

Any occurrence of NP 1.0 product events should be actively collected during the study and documented by the study site. Nicotine pouch 1.0 product events will be categorized into:

- Nicotine pouches not extractable from can/sticking together
- Rupture of the nicotine pouch when using
- No release of flavor when using
- No release of nicotine when using, or
- Other

Furthermore, any product event that leads to an AE/SAE will follow the same processes as described in section 8.2.

Confidentiality Statement

Confidential Page 62 of 98

Related to QMS-0017588

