9.7 Early Termination Procedures

When a subject is discontinued from the study, all early termination procedures listed in Table 9 are performed unless the subject refuses to perform the assessments or the procedures have already been performed during that study day. Early termination procedures are to be performed only for subjects who have been exposed to investigational products. After the date of termination, the subject will enter into the 3-day Safety follow-up period.

Confidentiality Statement

Confidential Page 72 of 98

Related to QMS-0017588

Document ID: VV-TMF-00821

Blood Sample	Procedures	Additional Information
Х	Clinical laboratory parameters (hematology, clinical chemistry)	Section 7.6.1
	Urine analysis safety panel	Section 7.6.1
	Urine pregnancy test (all female subjects)	Section 7.6.5
	Vital signs	Section 7.4.5
	ECG	Section 7.4.7
	Physical examination	Section 7.4.3
	Information on the risks of smoking/advice on smoking cessation and debriefing on NP 1.0	Section 7.2
	AE/SAE, concomitant medication recording	Section 8.2
	Product events	Section 8.7

Table 9Early Termination

Abbreviations: AE = Adverse event; ECG = Electrocardiogram; SAE = Serious adverse event

Confidentiality Statement

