8.8 Vital Signs

Vital signs (systolic and diastolic blood pressure, pulse rate, and respiratory rate) will be measured at Screening, Admission (Day -1), Day 1 to Day 3 prior to T_{0M}. If applicable, an early termination assessment will be performed.

All parameters will be recorded in supine position after the subject has rested for at least 5 minutes. Subjects should have abstained from using any nicotine/tobacco containing products for at least 15 minutes prior to the assessment.

For those results outside of the normal range, the Investigator will determine appropriate follow-up including reporting of any AEs.

Descriptive statistics will be reported for vital signs measurements (blood pressure, pulse, respiratory rate) by study day. Change from baseline will be summarized in a similar manner. Baseline is defined as the result closest and prior to the first product administration, which may include unscheduled or recheck results. This will typically be the result collected prior to T_{0M} on Day 1. Post product use unscheduled events or rechecks will not be included in summaries. Similarly, early termination results will not be included in summaries.

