8.9 Electrocardiogram

An ECG will be recorded at Screening, Admission (Day -1), and at Day 3. If applicable, an early termination assessment will be performed.

The ECG testing will be performed as per the investigational site standard practice. A standard 12-lead ECG will be recorded after the subject has rested for at least 10 minutes in supine position.

Statistical Analysis Plan Number CA36095

The following parameters will be documented: heart rate, PR interval, QRS interval, QT interval, and QTc interval, corrected by the ECG device according to Fridericia's formula [QTcF]. Every ECG has to be assessed as normal, abnormal – not clinically significant, or abnormal – clinically significant.

Descriptive statistics will be presented for each ECG parameter by study day. Change from baseline will be summarized in a similar manner. Baseline is defined as the result closest and prior to the first product administration, which may include unscheduled or recheck results. This will typically be the result collected at Admission (Day -1). Post product use unscheduled events or rechecks will not be included in summaries. Similarly, early termination results will not be included in summaries. QTcF values that are > 450 msec or increase from baseline > 30 msec will be flagged in the data listing.

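### Early-termination results are left out of the laboratory, vital-sign and ECG summary tables, so a subject stopped before the Day 3 assessment has no laboratory or ECG change from baseline there

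*SAP*

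**What the plan says.** The exclusion in SAP 8.7 reads "Similarly, early termination results will not be included in summaries", and SAP 8.8 (vital signs) and 8.9 (ECG) carry the same sentence. The sentence before it closes the other route by which such a value could enter: "Post product use unscheduled events or rechecks will not be included in summaries".

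The scheduled assessments are:

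- **Laboratory (SAP 8.7):** at Screening, on Day -1, "and at Discharge (Day 3), or an early termination assessment will be performed, as applicable".
- **ECG (SAP 8.9):** "An ECG will be recorded at Screening, Admission (Day -1), and at Day 3".
- **Vital signs (SAP 8.8):** these "will be measured at Screening, Admission (Day -1), Day 1 to Day 3 prior to" the morning product use. SAP Table 4.3 also lists a Day 3 discharge reading.

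On who has early-termination assessments, protocol 8.6 says: "Subjects who are discontinued from the study because of an AE will undergo the early termination procedures". Protocol 9.7 adds: "Early termination procedures are to be performed only for subjects who have been exposed to investigational products". Table 9 of the protocol includes laboratory tests, urinalysis, vital signs and ECG in that set. Section 9.7 also waives any procedure already done on the same study day.

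On reporting, the opening of SAP 8 lists all CRF data, early-termination results included. Protocol 8.4 sends clinically significant abnormal findings to the adverse-event record. Protocol 12.7 says that safety data will, in general, be both listed and tabulated in the Safety population, and it states no exclusion for early termination. SAP 9 names two changes from the protocol (VAS AUCs and spirometry ranges) and declares everything else aligned.

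**The concern.** Changes from baseline in laboratory values, vital signs and ECG are stated safety endpoints. For laboratory tests and ECG the plan has one scheduled post-exposure time, and SAP 8.7 itself presents the early-termination assessment as the alternative to it. Appendix A of the protocol puts the two in one column. The summary rule keeps one of the pair and drops the other.

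A subject stopped before Day 3 can therefore count in the baseline row and have nothing after it, even though a post-exposure value was taken. Subjects stopped for an adverse event are part of this group, so readers of the change tables would want to see their values beside the rest. Adverse-event tables count events. They do not show the size of a change in QTcF, heart rate or a laboratory parameter. The protocol also says that the test product has not previously been used in humans.

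**Working it through.** The plan gives no figure to reproduce. The check is textual, followed by a simple illustration.

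**Step 1. What reaches the tables, by time of stopping.**

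| Subject stops | Laboratory and ECG tables | Vital-sign tables |
|---|---|---|
| After the Day -1 product test | Baseline only | Baseline only |
| Day 1, after morning use | Baseline only | Day 1 pre-use reading, which SAP 8.8 usually treats as baseline |
| Day 2, after the morning reading | Baseline only | Day 2 reading, taken after Day 1 use, is kept; a later early-termination reading is not |
| Day 3, after the morning blood sample | Haematology and chemistry kept; urinalysis and ECG only if already done | Day 3 pre-use reading kept |

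The last row rests on protocol 12.7, which puts the Day 3 safety laboratory assessments in the morning before product use, and on the same-day waiver in 9.7.

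**Step 2. Whether an early-termination value exists.** No laboratory test or ECG is scheduled on Day 1 or Day 2. The waiver therefore does not apply on those days, and the tests are taken unless the subject refuses. The position is less certain in two cases:

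- On Day -1, laboratory tests, vital signs and ECG are all done before enrollment (protocol Table 5). Read literally, the waiver would allow the site to skip them again after the product test.
- Vital signs are taken each morning on Days 1 to 3, so the same reading applies to them.

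In either case the tables have no post-exposure value from early termination: it was excluded or it was never taken.

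**Step 3. Illustration of size.** The documents give no early-stop rate, so the inputs below are assumptions. With 24 randomized and, in general, no replacement after randomization (SAP 3.3), *k* stops before the Day 3 assessment leave 24 − *k* subjects in that row:

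- *k* = 1: n = 23, loss 1/24 = 4.2%
- *k* = 2: n = 22, loss 2/24 = 8.3%
- *k* = 3: n = 21, loss 3/24 = 12.5%
- *k* = 4: n = 20, loss 4/24 = 16.7%

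With independent stops at rate *d*, P(at least one) = 1 − (1 − *d*)^24, and P(two or more) = 1 − (1 − *d*)^24 − 24*d*(1 − *d*)^23:

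| Assumed *d* | At least one | Two or more |
|---|---|---|
| 2% | 38% | 8% |
| 5% | 71% | 34% |
| 10% | 92% | 71% |

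The Safety population may exceed 24, because it includes subjects exposed only in the product test (SAP 4.1.2). The percentages describe randomized subjects only.

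**Step 4. Protocol against SAP.** Protocol 12.7 states no exclusion, and SAP 9 declares none. Protocol 12.1 leaves full detail to the SAP but also requires changes to the planned methods to be documented there.

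**The case against.** The best defence is comparability. The tables are organized by study day, and early-termination values are taken under other conditions. Laboratory samples may be non-fasting, whereas Day 3 samples follow a 10-hour fast (protocol 7.6.1 and Appendix A). The Day 3 ECG is set at 60 ± 10 minutes after the start of use, whereas early-termination procedures follow as soon as practical. Scheduled vital signs on Days 1 to 3 are pre-use, and early-termination readings may not be. Pooling them with Day 3 would blur the Day 3 row. This stands, and it rules out a combined last-value row. It does not rule out a separate row.

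The second defence is that the signals are visible elsewhere. Adverse-event tables keep these subjects and include a summary of events leading to study discontinuation. Out-of-range laboratory values are listed, and QTcF above 450 msec or an increase above 30 msec is flagged in a listing. With 24 randomized subjects, listings can be read one by one. This also stands, and it makes the point a small one. An early-termination change still appears in no summary table.

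Third, protocol 12.7 is hedged and the SAP is meant to supply detail, so the rule is not a plain contradiction of the protocol. That is fair. The point is only that SAP 9 does not mention it.

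A reader might go further and infer that these tables describe completers only, or that everyone stopped for safety disappears from them. The documents do not support either reading. A subject who stops on Day 2 after the morning reading, or on Day 3 after the blood sample, is a non-completer who still contributes scheduled values.

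**Conclusion.** The point holds as a limited reporting gap. In the laboratory and ECG summary tables, a subject stopped before the Day 3 assessment has no post-exposure value and no change from baseline. In the vital-sign tables any early-termination reading is dropped, while earlier scheduled readings may remain. SAP 9 does not record the rule as a departure from protocol 12.7.

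It would be wrong to infer that the data are lost or that the safety tables as a whole ignore these subjects: the values that were taken are listed, and clinically significant abnormalities enter the adverse-event tables. The number affected is unknown. The early-stop counts and rates above are assumptions, and nothing in the documents shows how many stops would be for adverse events. The study is exploratory, and laboratory and ECG results are tabulated by day after several products, so no product comparison depends on this. It is a low-cost improvement rather than a threat to the conclusions.

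**What to change.** Keep the by-study-day rows as they are. Then:

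- Add a separate 'Early termination' row, giving the value, the change from baseline and n, to the laboratory, vital-sign and ECG tables.
- Footnote that early-termination laboratory samples may be non-fasting, and that ECG and vital signs in that row are not at a fixed time from product use.
- Record in SAP 9 how early-termination results are summarized relative to protocol 12.7.

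The cost is one row per table, using results already due to be collected. The drawback is that the row will have a small n and mixed assessment conditions, so it should be read as description only. It cannot recover a value where the same-day waiver meant that no assessment was made.

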8.8 Vital Signs

Vital signs (systolic and diastolic blood pressure, pulse rate, and respiratory rate) will be measured at Screening, Admission (Day -1), Day 1 to Day 3 prior to T_{0M}. If applicable, an early termination assessment will be performed.

All parameters will be recorded in supine position after the subject has rested for at least 5 minutes. Subjects should have abstained from using any nicotine/tobacco containing products for at least 15 minutes prior to the assessment.

For those results outside of the normal range, the Investigator will determine appropriate follow-up including reporting of any AEs.

Descriptive statistics will be reported for vital signs measurements (blood pressure, pulse, respiratory rate) by study day. Change from baseline will be summarized in a similar manner. Baseline is defined as the result closest and prior to the first product administration, which may include unscheduled or recheck results. This will typically be the result collected prior to T_{0M} on Day 1. Post product use unscheduled events or rechecks will not be included in summaries. Similarly, early termination results will not be included in summaries.

8.9 Electrocardiogram

An ECG will be recorded at Screening, Admission (Day -1), and at Day 3. If applicable, an early termination assessment will be performed.

The ECG testing will be performed as per the investigational site standard practice. A standard 12-lead ECG will be recorded after the subject has rested for at least 10 minutes in supine position.

Statistical Analysis Plan Number CA36095

The following parameters will be documented: heart rate, PR interval, QRS interval, QT interval, and QTc interval, corrected by the ECG device according to Fridericia's formula [QTcF]. Every ECG has to be assessed as normal, abnormal – not clinically significant, or abnormal – clinically significant.

Descriptive statistics will be presented for each ECG parameter by study day. Change from baseline will be summarized in a similar manner. Baseline is defined as the result closest and prior to the first product administration, which may include unscheduled or recheck results. This will typically be the result collected at Admission (Day -1). Post product use unscheduled events or rechecks will not be included in summaries. Similarly, early termination results will not be included in summaries. QTcF values that are > 450 msec or increase from baseline > 30 msec will be flagged in the data listing.

8.10 Prior and Concomitant Medications

All prior and concomitant medications will be listed by subject. Anatomical Therapeutic and Chemical (ATC) codes (World Health Organization Drug Dictionary) using the version defined in the DMP. Concomitant procedures recorded during the study will be listed by subject. Concomitant medications will be summarized using frequency count by product.

8.11 Physical Examination

A physical examination will be conducted at Screening, Admission (Day -1) and at the Day of Discharge (Day 3). If applicable, an early termination assessment will be performed.

All data found in the CRF will be listed. Physical examination has to be assessed as normal, abnormal – clinically not significant, or abnormal – clinically significant. Change in physical examination from baseline will be discussed in the CSR.

8.12 Spirometry

Spirometry without bronchodilator will be performed at the Screening visit in accordance with the 2019 guideline of the American Thoracic Society (ATS)/European Respiratory Society (ERS) Joint Task Force on the standardization of spirometry (Graham, B.L., et al., 2019). Spirometry predicted values will be standardized to the National Health and Nutrition Examination Survey III predicted set.

Every Spirometry has to be assessed as normal, abnormal – clinically not significant, or abnormal – clinically significant.

For those results outside of the normal range, the Investigator will determine appropriate follow-up including reporting of any AEs.

Assessed parameters will include: Forced expiratory volume in 1 second (FEV1), FEV1 % predicted, Forced vital capacity (FVC), FVC % predicted, and FEV1/FVC.

Spirometry parameters will be listed by subject and summarized using descriptive statistics.

8.13 Cytochrome P450 2A6 (CYP2A6) Activity

CYP2A6 activity drives the metabolism of nicotine to cotinine and subsequent metabolites. CYP2A6 activity will be measured in plasma using the metabolic molar ratio of trans-3'-hydroxycotinine/cotinine.

On Day -1, one blood sample will be collected for determination of CYP2A6 activity (cotinine and trans-3'-hydroxy-cotinine) prior to the NP 1.0 product test.

Individual results will be listed and descriptive statistics will be presented for the SAF and PK population.

9. SUMMARY OF CHANGES FROM PROTOCOL-PLANNED ANALYSIS

In section 7.2 AUCs related to T1 to T11 for VAS craving assessment, VAS liking assessment and VAS satisfaction assessment have been added to the descriptive statistics.

In section 8.12, it is specified that the investigator will define ranges to determine normal or abnormal Spirometry results.

All other analyses described in this SAP are aligned with those analyses described in the protocol.

Statistical Analysis Plan Number CA36095

